6 It is intuitive that post discharge surgical complications are associated with
7 increased patient dissatisfaction, and directly associated with an increase in medical
8 expenditures. It is also easy to make the connection that many post hospital discharge
9 surgical complications including surgical site infections could be influenced or
10 exacerbated by patient co-morbidities. The authors of a recent study reported that female
11 gender, obesity, diabetes, smoking, hypertension, coronary artery disease, critical limb
12 ischemia, chronic obstructive pulmonary disease, dyspnea, and neurologic disease were
13 all of among significant predictors of surgical site infections after vascular reconstruction
14 was performed. The main concern for optimal patient care especially in geographically
15 isolated areas of West Virginia is to have early, expeditious, and prompt diagnosis of
16 early surgical site infection with subsequent indicated interventions. This theme will lead
17 to patient satisfaction, minimizing third party interventions and decrease the total cost
18 associated with these complications. Nevertheless, it seems reasonable to believe that
19 monitoring using telehealth technology and managing the general health care patients
20 receive after a hospital vascular intervention will improve overall health and reduce post-
21 operative complications.
22

23 **Aims/Objectives:**
24

- 25 1. The primary objective of the current project is to compare early and late
26 outcomes for patients who receive post discharge health care monitoring
27 (which includes using **Telehealth electronic monitoring; THEM**) to patients
28 who receive **standard of care (SOC)** and routine discharge instructions and no
29 monitoring.
30

31 **Methods:**
32

- 33 1. Randomize patients who are scheduled to have revascularization
34 interventions with groin incisions to receive either telehealth electronic health
35 care monitoring or normal standard of follow-up care.
36 2. Follow patients for 4 weeks, record any 30-day hospital readmissions or
37 complications. In addition, have participants complete the follow-up survey
38 questionnaires.
39
40
41
42
43
44
45

1 **Background:**
2

3 Postoperative hospital readmissions present significant challenges for patients and
4 health care systems as well. There is significant Medicare expenditure devoted to this
5 issue. Although it is intuitive to assume that these issues can be prevented to minimize
6 cost, but the problem continues to escalate in many aspects. A recent report indicated
7 that Medicare expenditures were associated with a readmission rate estimated to be \$12
8 billion per year.¹ Another report² has indicated that about 24% of the entire Medicare
9 expenditure is consumed by readmissions. Ironically, those reports were based on data
10 gathered between 1974 to 1977, and definitely would be much higher in today
11 calculations according to current inflation index in GDP. As health care professionals,
12 we should be aware of all ongoing ramifications associated with readmissions, as the
13 integral scope of proper patient care is under scrutiny with all its related issues such as,
14 hospital reimbursement, physician credentialing process and regulation, referral pattern
15 and eventually educational enterprises.³
16

17 **Surgical Site Infections Following Arterial Revascularization with Groin Incision**
18
19

20 Vascular surgery especially arterial revascularizations with groin incisions
21 (ARGI) has always been associated with the potential of higher rates of readmission
22 pertaining to high-risk patients with multiple co-morbidities such as diabetes, cardiac
23 issues and poor general nutrition. These types of issues are more demanding in
24 geographical areas such as rural West Virginia where easy access to medical attention is
25 not available. In most cases, 30 day-readmissions are considered to be in-hospital
26 complications. However, some authorities have suggested that readmissions after
27 vascular interventions are really measures of post discharge complications rather than in-
28 hospital complications.³⁻⁸ Most U.S hospitals are currently in full compliance with the
29 Surgical Care Improvement Project (SCIP). Unfortunately, compliance with these
30 processes has not yet directly been associated with reduced SSI rates.^{9,10} In addition,
31 reports of 30-day readmission rates for vascular surgery patients are very high and it may
32 vary from 11 to 25%.^{1,8}
33

34 Identifying patients with higher rates of readmission after discharge is of essence
35 in order to pay more attention or even to deploy a system to monitor them closely. In one
36 study,¹¹ patients with a positive clinical culture obtained more than 48 hours after hospital
37 admission had an increased hazard of readmission (HR, 1.40; 95% CI, 1.33-1.46) after
38 adjusting for other co-morbidities. Another review indicated that SSIs may develop in
39 10% of the 3,663 patients who underwent an inpatient general surgical procedure. It has
40 been reported that diagnosis of SSI after discharge was also associated with a high
41 readmission rate despite occurring in healthier patients. It has been proposed that
42 discharge specific instructions related to wound infections along with a wound
43 surveillance in-clinic visit within the first week may result in a decreased readmission
44 rate.⁷ Gohil et al assessed 30-day readmission rates from 323 hospitals and reported that
45 infection-related readmissions accounted for 28% of all readmissions. The same study
46 reported that academic hospitals had higher all-cause and infection-related readmission

1 rates.¹²

2
3 The thought of reducing readmission and infection rates has been energized by the
4 recent policy proposals suggested by the Medicare Payment Advisory Commission to
5 lower average per-case reimbursements to hospitals with high (risk-adjusted) rates of re-
6 hospitalizations. It is important to identify high-risk patients in order to be more focused
7 and to incorporate procedures to identify early signs of infection. This approach of
8 increased outpatient support has been proven to be cost effective.² Some researchers have
9 developed a scoring system to accurately identify patients at high risk for 30-day
10 unplanned readmissions and suggested this could help direct discharge and home health
11 care resources to patients, which ultimately could be used to reduce readmissions and
12 improving efficiency.⁸ Gibson et al reported that diagnosis of surgical site infection (SSI)
13 after discharge is associated with a high readmission rate despite occurring in healthier
14 patients.⁷ The authors of a recent study reported that female gender, obesity, diabetes,
15 smoking, hypertension, coronary artery disease, critical limb ischemia, chronic
16 obstructive pulmonary disease, dyspnea, and neurologic disease were all of among
17 significant predictors of SSI after vascular reconstruction was performed.¹³ Another
18 important potential impact of telehealth technology is that it may minimize the burden
19 and cost of 3rd party home visits to evaluate wounds or provide treatment. Currently,
20 many interventions of vascular surgery require postoperative visiting nursing service
21 (VNS) to evaluate wound or treatment at home. The home visit approach utilizes
22 significant resources to achieve its target. As part of the main objectives of telehealth
23 technology, we believe that our suggested approach will limit not only the number but
24 also the frequency of VNS. In addition it may even supersede VNS as it provides to some
25 extent more continuous and more objectives measures to provide a better follow up to our
26 patients after discharge.

27
28 In conclusion, it seems reasonable to believe that monitoring using telehealth
29 technology and managing the general health care patients receive after a hospital vascular
30 ARGI intervention will improve overall health, patient care and will reduce post
31 operative complications. Our project will be conducted to directly give more and
32 continuous attention to postoperative period after hospital discharge. We believe that
33 early readmission is a “failed discharge” as has suggested by others. This matter is of
34 great interest particularly to our specialty.

35 36 37 **Objectives**

38 The primary objective of the current project is to compare outcomes for patients
39 who receive post discharge health care monitoring (which includes using Telehealth
40 electronic monitoring; THEM) to patients who receive standard of care (SOC) and routine
41 discharge instructions and no monitoring.

42 **Outcomes**

43 The primary outcomes include 30-day readmissions, post-operative complications
44 and access site/wound infections. Secondary outcomes will include a pre and post
45 surgery quality of life measures (SF-8) and patient satisfaction (>30-day) along with an
46 occurrence of any 30-day stroke, MI or death.

1
2
3 **Study hypotheses:**
4

- 5 1. A smaller percentage of THEM patients will require a 30-day unplanned
6 readmission.
7 2. A smaller percentage of THEM patients will develop a SSI.
8 3. THEM patients will report greater post discharge satisfaction and higher
9 quality of life measures.

10
11 **Significance:**
12

- 13 1. Information and results obtained from this study may suggest additional post
14 discharge treatment approaches which in turn could lower 30-day
15 readmissions and complications for patients undergoing surgery.
16
17 2. Likewise, information and results obtained from this study could be used to
18 help promote greater patient satisfaction and quality of life measures.
19
20 3. This approach may impact some direct cost pertaining to post-discharge
21 follow-up as visiting nurse services. THEM approach will provide a direct,
22 measurable, specific tool to provide therapy related information to the treating
23 physician during post-discharge period.
24

25
26 **Study Design:**
27

28 The current study is designed to be a **prospective, randomized, open-label, single-**
29 **center with blinded endpoints (PROBE) study.**¹⁴ More specifically, it is designed to test
30 the hypothesis that Tele-health monitoring will decrease 30-day readmission and
31 complication rates. Patients with planned vascular ARGIs will be consented for possible
32 inclusion. Patients who give their consent will be enrolled and randomly assigned to one
33 of the two treatment arms: 1) standard of care (SOC) or 2) Tele-health electronic
34 monitoring (THEM) using TeleMed 2020 home health monitoring system.
35 The primary endpoints will be measured as simply the occurrence or not of any
36 unplanned 30-day readmission and/or complication (0/1). Patients in the intervention
37 group (THEM) will receive a tablet computer and home monitoring medical devices with
38 sensors to transmit the information to a central website that will be monitored by care
39 managers. Medical devices will include weight scales, blood pressure cuffs and oxygen
40 saturation monitors. Clinical care managers will remotely monitor the patients and all
41 electronic readings. Clinical care managers will call or send electronic messages to the
42 patients based on alerts generated by the tele-health monitoring system.
43

44 **Sample:**

1
2 The population for this study will be patients with any planned vascular procedures with
3 cut-down access to the groin and will be treated by one of the Vascular Surgeons in the
4 Vascular Center of Excellence (VCOE).

5
6 *Sample Size:*

7 The sample size was estimated based on the readmission rates from a previous research
8 study. An overall sample size of 200 subjects will have 80% power to detect a reduction
9 in the 30-day infection/readmission rate from ~12 in the SOC group to ~2% in the THEM
10 group using a 2-sided α of 0.05. We expect a 10% drop-out rate and thus plan to enroll
11 110 patients in each group (N=220 overall).

12
13
14 *Inclusion/exclusion criteria:*

15 Patients meeting the inclusion criteria, which is any planned vascular procedures with
16 cut-down access to the groin and treated by one of the Vascular Surgeons in the Vascular
17 Center (VCOE) will be consented and enrolled. Patients will be excluded for any of the
18 following reasons (1) do not plan to do follow-up visit at the VCOE; (2) inability to sign
19 or understand the consent form; (3) do not have home internet service with WIFI or live
20 outside of the provided cell coverage area (cell coverage will be provided for patients
21 without internet WIFI). Informed consent will be obtained research coordinator; eligible
22 patients will be randomly assigned to either the treatment group (THEM) or the control
23 group (SOC).

24
25
26 *Randomization:*

27 The randomization will be done centrally using a computer containing a SPSS algorithm.
28 The randomized list will be placed in 220 envelopes and labeled 1 through 220. After
29 randomization and necessary medical procedures, but before discharge each patient
30 depending on treatment assignment will receive either the home monitoring equipment
31 with instruction for those in the treatment group (THEM) or normal discharge
32 instructions for the control group (SOC).

33
34 Patients in the intervention group will receive a tablet computer and home monitoring
35 medical devices with sensors to transmit the information to a central website that will be
36 monitored by care managers. The TeleMed 2020 electronic home health monitoring
37 system will be used to provide constant surveillance of THEM patients. In addition, the
38 tablets will have the ability to send a high resolution photograph of wound if needed.
39 Medical devices will include weight scales, blood pressure cuffs, thermometers and
40 oxygen saturation monitors.. Clinical care managers will remotely monitor the health of
41 patients by viewing all electronic readings. Study care managers will call or send
42 electronic messages to the patients based on alerts generated by the tele-monitoring
43 system. The main focus of this approach is to have a direct, specific, objective and
44 measurable assessment of any early wound infection after lower extremity
45 revascularization. The care manager will make direct electronic communication as to the

1 appearance of the access wound and if needed request that a picture be sent for
2 observation.

3 4 **TeleMed 2020**

5
6 Bloomberg Business Company Overview of TeleMed 2020, Inc.

7 8 Company Overview

9 TeleMed 2020, Inc. owns and operates a cloud-based SaaS solution for remote patient
10 monitoring. The company allows clinician scheduling and ongoing patient capture and
11 sharing of critical information yielding earlier and more active care plan management.

12 The company is based in Indianapolis, Indiana.

13
14 <http://www.bloomberg.com/research/stocks/private/snapshot.asp?privcapid=310873357>

15
16
17 For the THEM group, the care manager will:

- 18
19 1. Monitor patient vital signs: daily weight, blood pressure, pulse, , oxygen
20 saturation and temperature
- 21 2. Ask about the description of the postoperative wound site: including any
22 surrounding erythema, discharge, wound dehiscence and healing. If necessary,
23 ask for a picture of the wound site to be sent. A transmitted photograph of the
24 wound condition may augment amount of knowledge available to clinical care
25 management team.
- 26 3. Complete a target organ evaluation: which means to evaluate the bypass and this
27 will include general feeling, pain (location, degree, type and relieving elements).
- 28 4. Assess compliance with the discharge medications.

29
30
31 Early signs of infection would include, but not be limited to fever, tachycardia,
32 discharge, erythema, wound dehiscence, and pain. All of these will be evaluated via
33 telecommunication tools by the care manager and if needed immediately discussed with
34 supervising physician. In addition, the patient, if needed, will be scheduled for an early
35 office visit and/or re-hospitalization.

36
37 For the SOC group, the care manager will follow the current standard of care.

38 39 40 **Procedure:**

41 **PRE-TREATMENT:**

- 42 • Patients will be identified by the Vascular Surgeon and scheduled for the
43 procedure.
- 44 • Study coordinator will review patient scheduling records to identify
45 potential study participants.

- The study coordinator will explain the research study and the informed consent with the patient prior to the surgical intervention.
- The patient upon appropriate consent signs and dates the consent form and the HIPPA authorization form, which is attached to the consent form.
- Patient upon informed consent is randomized to either receive the treatment (THEM) or to the SOC control group (SOC).
- Complete a pre-treatment SF-8 and baseline history form.

Quality of life measure

The SF-8™ Health Survey is a brief and comprehensive quality of life population survey. It has only eight questionnaire items, and by design according to the company’s website “was constructed to replace the SF-36® and SF-12® in population health surveys in the U.S. and internationally. Accordingly, it has been translated and linguistically validated for use in more than 30 countries and languages using IQOLA Project methods. It has been adopted by federal agencies (e.g., the DOD), leading polling organizations (e.g., the Roper-Starch Worldwide Health Report), and industry sponsors of clinical trials and effectiveness research (e.g., Glaxo Smith Kline, Johnson & Johnson, and Searle).” In addition, the validation and norming measures of the SF-8™ Health included the general population as well as many subgroups of subjects with co-morbidities such as depression and diabetes. The SF-8™ is a very sensitive test that has both test/retest reliability as well as the ability to detect change of time. The scoring of the SF-8™ produces two summary scores. One for the physical (PCS) and one for the mental dimension (MCS). It also provides the same 8 subscale scores for each dimension as the SF-36.

Vascular Intervention:

All patients will receive their planned and scheduled procedures.

Follow-Up Protocol:

After 2-4 weeks, all patients will have a follow-up visit scheduled at the VCOE clinic. Follow-up will include physical exam including a routine visual inspection of access site wound and comments will be collected. All patients will complete a second SF-8 survey form and a patient satisfaction survey. If follow-up visit is less than 30 days, then a member of the study team will call patients and obtain SF-8, satisfaction survey and follow-up form.

Data Collection:

Will include (see appendix):

- 1) Signed consent forms
- 2) Enrollment and demographics form
- 3) SF-8 survey
- 4) Patient satisfaction survey
- 5) 4 week follow-up form

Schedule of Events

Information:	SOC	THEM
Sign Informed Consent	Pre-Intervention	Pre-Intervention
Randomization	Pre-Intervention	Pre-Intervention
Pre-treatment	SF-8 survey	SF-8 survey
Equipment & instructions	At discharge	At discharge
Follow Up:		
Special issue follow-up	Patient initiated	Patient or monitor initiated
Routine follow-up exam	2-4 weeks	2-4 weeks
	SF-8 survey	SF-8 survey
	Satisfaction survey Follow-up form Debriefing	Satisfaction survey Follow-up form Debriefing

1
2
3
4
5
6
7
8
9
10
11
12
13
14
15
16
17
18
19
20
21
22
23
24
25
26
27
28
29
30
31

SOC = Standard of Care
THEM = Tele-Health Electronic Monitoring

Statistical Analysis:

All analyses will be based on intention-to-treat (ITT) analyses. However, if possible we will sub-analyze the data on a per-protocol basis as well. Descriptive statistics will be expressed in terms of frequencies, percentages, or means \pm standard deviation (SD). Categorical variables will be tested by chi-square or Fisher exact tests and continuous variables will be tested by student t-test or paired t-test for pre/post measures, where deemed appropriate. Survival and freedom from event curves such as freedom from re-admission will be created using the Kaplan Meier method, compared by the Log Rank test, and graphically presented using life tables. All probability values will be 2 sided and ‘p’ values <0.05 will be considered significant. Statistical analyses will be performed using SPSS version 19.0 for Windows. This study will be registered at ClinicalTrials.gov.

End Points:

The primary outcomes include 30-day readmissions, post-operative complications and access site/wound infections.

Secondary outcomes will include a pre and post-surgery quality of life measures (SF-8), patient satisfaction (>30-day) and number of VNS visits along with an occurrence of any 30-day stroke, MI or death.

Definitions:

1
2 Event-free survival will be defined as the freedom from unplanned 30-day
3 readmission and/or 30-day access site wound infection.

4
5 **Human Subjects**

6 **Recruitment Method(s)**

7
8 The current study protocol received approval from our local institutional review
9 board. The study group participants will sign consent papers on admission to the
10 vascular lab when the patient presents for pre-procedure evaluation. The study care
11 manger will identify potential study participants, and provide information about the
12 study. Study staff will be trained and knowledgeable on the research protocol. This
13 study will not offer any direct benefit for the study participants. Staff will not begin
14 consenting patients until they have completed this training and are in compliance with
15 any pertinent trainings offered by Research and Grants.

16
17 **Payment/Costs of Testing:**

18
19 Patients enrolled in both study comparison groups (THEM and SOC) will not
20 incur additional expenses as a due to their participation in this study. Normal standard of
21 care will be provided to the participants in the SOC group, while the members of THEM
22 group will receive enhanced care management. The patient's insurance or the patient will
23 not be billed for any of the care management or Tele-health monitoring.

24
25 **Risk and Benefits:**

26
27 There are no known risks or benefits to the study patients. Data collection takes
28 place utilizing existing data that has been acquired during the delivery of routine medical
29 care

30
31 **SIDE EFFECTS**

32
33 **To date there are no know or expected side effects. Should other unknown risks
34 become available to the researchers; patients will be informed as soon as possible.**

35
36
37 **Adverse reactions**

38
39 **To date there are no know or expected side effects. Should other unknown risks
40 become available to the researchers; patients will be informed as soon as possible.**

41
42 **Confidentiality of Records:**

43
44 Records will be kept on all study participants according to standard routine
45 procedures. However, additional study variables will be collected. Electronic and data
46 collection sheets will be kept in strict confidence. Data collection sheets will be kept in a

1 locked area. Electronic data will reside on a secure CHERI server and will only be
2 accessible by appropriate research staff members.

3
4 **Compensation:**

5 Participation in this research study is strictly voluntary and participants will not be
6 reimbursed or paid for their participation.

7
8 **Debriefing:**

9 Participants will be treated with the same standard of care as all other patients.

10
11 **Interventions:**

12
13 Participants will follow the same standard of care as other patients requiring
14 treatment. If a study participant has any side effects, the patient will be evaluated by
15 their physician and a decision to continue or stop treatment will be made.

16
17 **Investigator Qualifications:**

18
19 [name]., FACS, RPVI, MPH, MBA
20 Associate Professor, Department of Surgery
21 Vascular and Endovascular Surgery Division
22 West Virginia University
23 [name]
24 [name]
25 Office: [contact]
26 [contact]
27 [contact]

28
29
30
31 **Other Participants:**

32 [name] BA will provide data analysis and interpretation support; he is an employee
33 of the CAMC Health Education and Research Institute.

34
35 A .5 FTE nurse will serve as study coordinator/clinical care manager.
36
37

1 **References:**

- 2

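### Allocation envelopes are not protected from the nurse who recruits and consents, and the baseline SF-8 is listed after randomisation: an unguarded risk of selection bias

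*Combined protocol and SAP*

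**What the plan says.** The Randomization section has the list produced centrally by an SPSS algorithm. It continues: "The randomized list will be placed in 220 envelopes and labeled 1 through 220". Custody, sealing, opacity and order of opening are not mentioned.

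The people involved are described in several places:

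- Procedure (PRE-TREATMENT): "Study coordinator will review patient scheduling records to identify" candidates. The same coordinator explains the study and the consent form.
- Inclusion/exclusion criteria: "Informed consent will be obtained research coordinator; eligible" patients are then randomly assigned.
- Human Subjects, Recruitment Method(s): the study care manager "will identify potential study participants, and provide information about the" study.
- Other Participants: "A .5 FTE nurse will serve as study coordinator/clinical care manager". This is the only statement of who fills these posts.

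Patients are excluded for the "following reasons (1) do not plan to do follow-up visit at the VCOE; (2) inability to sign" or understand the consent form, or (3) for lack of home internet or cell coverage. For the THEM arm, the care manager reviews daily vital signs, asks about the wound, evaluates the bypass, checks medication compliance and responds to alerts.

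Procedure (PRE-TREATMENT) lists randomisation on consent and then, as the next item, the pre-treatment SF-8. The Schedule of Events table uses the same order.

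**The concern.** Concealment of allocation requires that whoever decides that a patient is eligible cannot know or foresee the next assignment. Here the two roles on either side of that line are given to one nurse, and two of the three exclusions are settled in conversation with the patient. Whether someone plans to return to the clinic, or understands the form, leaves room for discretion. If the next assignment were known, that discretion could shift the kind of patient entering each arm.

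The trial's other protections come too late. Intention-to-treat analysis covers only patients who were randomised, so it cannot restore those turned away beforehand. Blinded endpoint assessment guards how outcomes are judged, not who is enrolled.

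The SF-8 raises a related problem. Quality of life before and after surgery is a secondary outcome. If the baseline form is completed once the arm is known, the baseline itself may carry a reaction to the assignment.

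**Working it through.** **Reproducing the plan's own figure.** The Sample Size section gives about 12% (SOC) against about 2% (THEM), two-sided alpha 0.05, 80% power and 200 evaluable patients. With pooled variance and no continuity correction:

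n per arm = [1.96·√(2·p̄·(1−p̄)) + 0.8416·√(p1(1−p1) + p2(1−p2))]² / (p1−p2)², with p̄ = 0.07

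= [1.96·√0.1302 + 0.8416·√0.1252]² / 0.10² = (0.7072 + 0.2978)² / 0.01 ≈ 101.0, rounded up to 102.

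That is 204 in total against the stated 200; power at 100 per arm is 79.6%. The sample size reproduces and this point does not affect it. At the planning rates, 100 per arm gives 12 + 2 = 14 expected events.

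**Following one patient through the text.**

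| Step | Who | Safeguard stated |
|---|---|---|
| Identify | Surgeon, coordinator, care manager | None recorded; no screening log in the Data Collection list |
| Apply exclusions | Not assigned explicitly; consent is by the coordinator | No dated eligibility record required before assignment |
| Consent | Coordinator | Signed and dated form |
| Assign | Numbered envelope; holder and opener not stated | Numbering only |
| Baseline SF-8 | Not stated | Listed after assignment |
| Monitor THEM | Care manager | Not applicable |

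Under Other Participants, the coordinator and the care manager are the same half-time nurse. Numbering fixes a sequence but does not stop an envelope being read early. The word centrally describes how the list is made. It does not describe release of assignments one at a time, because the whole list then goes into envelopes.

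**Why an imbalance at entry would matter.** The documents give no figure for how far selection might shift risk, so the shifts below are assumptions. Suppose there is no true effect, overall risk is 12%, there are 100 patients per arm, and selection makes SOC baseline risk exceed THEM risk by d. The rejection probability is the sum of Bin(x; 100, 0.12 + d/2) × Bin(y; 100, 0.12 − d/2) over all x, y with |x−y|/100 ÷ √(p(1−p)·2/100) > 1.96, where p = (x+y)/200.

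| Assumed d | SOC vs THEM risk | Two-sided rejection |
|---|---|---|
| 0 points | 12% vs 12% | 5.1% |
| 2 points | 13% vs 11% | 7.3% |
| 4 points | 14% vs 10% | 14.1% |
| 6 points | 15% vs 9% | 26.0% |

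This shows how sensitive the test is to an entry imbalance. It says nothing about whether one would arise.

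**The case against.** The strongest reply is that the text is silent on custody, and silence is not access. A reader might infer that the nurse can see the next assignment. The documents do not say so: nothing gives the nurse the envelopes or makes their contents readable. That part of the reply stands, so the point is a missing protection and not a demonstrated breach.

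Second, the order of steps is a partial guard. Consent is signed and dated, and randomisation follows it. An enrolment form is also listed, and its content is in an appendix outside the text available here, so it may record eligibility. This stands in part, but it does not help if an assignment can be learned before eligibility and consent are settled.

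Third, the one-nurse reading rests on a single line. Elsewhere care managers are plural, the consenting role is called research coordinator, and the surgeon comes first: "Patients will be identified by the Vascular Surgeon and scheduled for the" procedure. The nurse is therefore not the sole gatekeeper. Even so, the staffing line is the only one given, and screening and consent still pass through the coordinator.

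Two further inferences are tempting and are not supported:

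- *A half-time nurse would gain by keeping patients out of THEM.* A patient turned away leaves the THEM envelope for the next one. The planned THEM total stays at 110, so exclusions would not reduce the number monitored.
- *Moving a few patients would produce a positive trial.* If 4 would-be events left THEM, 12 vs 8 per 100 gives z = 0.04/√(0.10·0.90·0.02) = 0.94, p = 0.35. Reaching p < 0.05 by chi-square takes 12 vs 4 (z = 2.09, p = 0.037), that is, removing 8 of 12. Nor could anyone pick out future events with certainty. If those turned away had twice the 12% risk (an assumption) and were replaced by average patients, each exclusion would remove 0.24 − 0.12 = 0.12 events, so removing 4 would take about 4/0.12 ≈ 33 exclusions.

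**Conclusion.** The point holds as an unguarded risk of selection bias. The plan uses numbered envelopes without required independent custody, sealing, sequential opening or eligibility recorded before opening. Its only staffing statement joins recruitment and consent to THEM monitoring in one person. Neither intention-to-treat analysis nor blinded endpoints can repair selection at entry.

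The size of any bias cannot be estimated from the documents, and no bias is shown. The conclusion rests on taking the staffing line at face value and on the visible text being complete on custody.

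The SF-8 part is narrower. It rests on the order of items in two lists. Equipment is handed over only at discharge, but nothing says that the arm is withheld from the patient until the baseline form is done.

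The plan should be changed on both counts. The stated sample size is unaffected.

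**What to change.** Amend the Randomization and Procedure (PRE-TREATMENT) sections, and align the Schedule of Events, as follows:

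1. An existing member of the research institute's staff holds the list, or holds sequential, sealed, opaque envelopes. This person does not recruit, monitor patients or assess endpoints and, where possible, does not analyse the data.
2. That person releases each assignment only after receiving a dated record that consent is signed, each exclusion has been answered and the baseline SF-8 is complete. This moves the SF-8 ahead of randomisation, which is a change to the listed order.
3. The holder logs the sequence number, date and patient ID at each release.
4. The coordinator keeps a log of all screened patients with the reason for any exclusion, so that exclusions can be compared with the allocation sequence.

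The cost is a wording change and one short call or e-mail per patient, 220 in all. Release would depend on office hours, which is workable because the procedures are planned. The documents name only data-analysis support at the institute. If that person is the only available holder, the analyst becomes unblinded to allocation, and the protocol should say so. The change has to be in place before patients are randomised, because concealment cannot be restored afterwards.
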